# List of Abbreviations and Definitions of Terms

AE	Adverse event
AESI	Adverse event of special interest
ANCOVA	Analysis of covariance
BMI	Body mass index
BoNT	Botulinum neurotoxin
BP	Blood pressure
BW	Body weight
СР	Cerebral palsy
CRO	Contract research organization
C-CASA	Columbia-Classification Algorithm for Suicide Assessment
C-SSRS	Columbia-Suicide Severity Rating Scale
DMC	Data Monitoring Committee
DSFS	Drooling Severity and Frequency Scale
eCRF	Electronic case report form
EDTA	Ethylene diamine tetra-acetic acid
EMA	European Medicines Agency
EudraCT	European clinical trial database
FAS	Full analysis set
FDA	Food and Drug Administration, USA
GCP	Good Clinical Practice
GICS	Global Impression of Change Scale
FIA	Fluorescence immunoassay
FIA-AB	Fluorescence immunoassay detecting antibodies
GMFCS	Gross Motor Function Classification System
HDA	Hemidiaphragm assay
HR	Heart rate
IB	Investigator's brochure
ICH	International Conference on Harmonization
ID	Intellectual disability
IEC	Independent ethics committee
IND number	Investigational new drug number (issued by the FDA)

IP	Investigational Product
IRB	Institutional review board
ISF	Investigator's site file
IU	International unit(s)
IWRS	Interactive Web Response System
LDU/kg	Lethal dose units per kilogram
МСН	Mean corpuscular hemoglobin
MCHC	Mean corpuscular hemoglobin concentration
MCV	Mean corpuscular volume
MedDRA	Medical Dictionary for Regulatory Activities
MMRM	Mixed Model Repeated Measurement
MRZ	Merz
mTDS	Modified Teacher's Drooling Scale
Ν	Number
OLEX	Open-label extension
PIP	Pediatric Investigation Plan
PPS	Per protocol set
SAE	Serious adverse event
SAP	Statistical analysis plan
SD	Standard deviation
SES	Safety evaluation set
SOP	Standard operating procedure
TBV	Total blood volume
TEAE	Treatment emergent adverse event
TEAESI	Treatment emergent adverse event of special interest
TESAE	Treatment emergent serious adverse event
U	Unit(s)
USAN	United States Adopted Name
uSFR	Unstimulated Salivary Flow Rate
V	Visit (number)

- Parent(s) In this protocol, the term parent(s) is used for any legally acceptable representative(s) including guardian(s), as defined in the ICH guideline E6 (R1) as individual or juridical or other body authorized under applicable law to consent, on behalf of a prospective subject, to the subject's participation in the clinical trial. Guardian(s) may replace parent(s) in the performance of study procedures. Note that where both parents have responsibility for the subject, both will be required to sign all documents where the parent's/parents' signature(s) is/are needed.
- Carer In this protocol, the term "carer" designates the person who spends the greatest amount of time with the subject and is in a responsible position for attending to and caring for the subject. This will often be a parent, but in some situations it may alternatively be a nurse, a day-care attendant or a day-care-center staff member with special responsibility for the subject.

## **1** SYNOPSIS

#### Study title

Prospective, randomized, double-blind, placebo-controlled, parallel-group, multi-center study with an open-label extension period to investigate the efficacy and safety of NT 201 in the treatment of children and adolescents (2–17 years) with chronic troublesome sialorrhea associated with neurological disorders, and/or intellectual disability.

#### Study phase

Phase 3

#### Indication

Chronic troublesome sialorrhea associated with neurological disorders (e.g. cerebral palsy, traumatic brain injury), and/or intellectual disability in children and adolescents aged 2–17 years.

#### Study objectives

The objective of this study is to investigate the efficacy and safety of NT 201 compared with placebo for the treatment of chronic troublesome sialorrhea associated with neurological disorders (e.g. cerebral palsy, traumatic brain injury) and/or intellectual disability in children and adolescents naïve to *Botulinum* neurotoxin treatment and aged 2–17 years. The total dose of NT 201 ranges from minimum 20 U to maximum 75 U or approximately 2 U/kg body weight depending on body weight classes. Subjects with a body weight  $\geq$  30 kg will receive a fixed total dose of 75 U. In this study, treatment-naïve subjects are defined as those who have not received BoNT treatment for this indication within the last 12 months.

#### Study population, diagnosis, and main criteria for inclusion and exclusion

Male and female children and adolescents will be recruited who are suffering from troublesome sialorrhea due to neurological disorders, and/or intellectual disability.

#### Main inclusion criteria:

- Male or female child/adolescent age 2–17 years.
- Any neurological disorder (e.g. cerebral palsy or traumatic brain injury) and/or intellectual disability associated with chronic troublesome sialorrhea for at least 3 months up to the screening. In subjects with intellectual disability (ID) without neurological disorders, a diagnosis of ID by a specialist, e.g. pediatrician or by a center for developmental medicine is required for inclusion.

- Severe drooling (modified Teacher's Drooling Scale [mTDS] ≥ 6; clothing occasionally becomes damp) as rated by the investigator.
- Parental consent and the subject's oral or written assent as the subject is able to provide.

Main exclusion criteria:

- Chronic troublesome sialorrhea not related to neurological disorders and/or intellectual disability.
- Body weight < 12 kg.
- Pharmacological treatment for sialorrhea or concomitant medication known to influence sialorrhea strongly (e.g. anticholinergics with exception of locally applied or short acting drugs used under general anesthesia) within 45 days before baseline and during the entire study period.
- Any previous known or suspected hypersensitivity to *Botulinum* toxin.
- Aspiration pneumonia within 6 month before screening.
- Any previous treatment with *Botulinum* toxin for any body region during the year before screening or within the screening period
- Prior, concomitant or planned surgery or irradiation to head and neck to control sialorrhea (including salivary gland surgery or salivary gland irradiation) within one year before screening or planned for any part of the entire study period.
- Concurrent diseases, including hematological, hepatic, renal, gastrointestinal, endocrine, pulmonary, musculoskeletal, or psychiatric diseases or conditions, which in the judgment of the investigator would put the subject at risk while in the study, could influence the results of the study, or negatively impact the subject's ability to participate in the study.
- Extremely poor dental and/or oral condition that might preclude safe study participation by the judgment of the investigator.
- Nursing mother or pregnant female subject.

#### Study design

*Main study period:* The main period of the study, comprising the screening period and one injection cycle (single treatment followed by 16 weeks for assessment in several visits to the study site) will take place for subjects aged 6–17 years according to a prospective, randomized, double-blind, placebo-controlled, parallel-group design, with active or placebo treatment (randomization ratio 2:1). Subjects aged 2–5 years will not be treated with placebo, but only with active treatment (NT 201) during the main period. The treatment will comprise four injections of NT 201 (parotid and submandibular glands, bilaterally); the dose is defined according to body weight (approximately 2 U/kg). At the end of the main period, subjects will be assessed for eligibility to enter the extension period.

*Extension period:* The main period will be followed by a 48-week, three-cycle extension period in which all subjects eligible for extension treatment will receive NT 201 ("open-label" treatment) according to the same per-body-weight formula. Dose reduction will be permitted in the third and fourth cycle if relevant adverse events occur. Treatment and observation will be similar to that of the main study period and will be concluded with an end-of-study examination at the end of the fourth cycle.

Data monitoring committee [DMC] and progressive reduction of lower age limit for subjects: Data will be subjected to continual review by an unblinded DMC. The first 30 subjects (age group 10 to 17 years) will be subjected to safety review when four weeks elapsed since the randomization of the last subject. This will be repeated after the recruitment of the next 30 subjects in this age group and then of the first 30 subjects in the age group 6–9 years. If in the above analyses no significant risk is identified by the DMC, then a next cohort can be opened and finally 30 children representing the youngest age group (2–5 years) will be enrolled. In parallel with this, recruitment and treatment of subjects in the age group 10–17 years and 6–9 years will continue. Children in the youngest age group will not be treated with placebo, but only with active treatment (NT 201) during all four injection cycles.

#### Planned study period

1st quarter 2015 to 2nd quarter 2019

#### Duration of treatment per subject

Each treatment is to be followed by an observation period of 16 weeks  $\pm$  2 weeks. Therefore, for all subjects, the total duration of all injection cycles will be 64 weeks (with permitted variation, 56–72 weeks).

#### Variables for analysis

#### Primary efficacy variables

For subjects aged 6–17 years the primary and co-primary variables are:

- Change in unstimulated salivary flow rate [uSFR] from baseline to Week 4.
- Global Impression of Change Scale [GICS] at Week 4 representing the functional improvement in drooling since baseline as assessed by the carer/parent(s).

## Secondary efficacy variables

For subjects aged 6–17 years:

- Change in uSFR from baseline to Week 8 and 12.
- GICS at Week 8 and 12.

Merz Pharmaceuticals GmbH MRZ60201_3091_1	SOP/245/EN - CLINICAL STUDY PROTOCOL Version 2.0 Version 16-JUN-2016

For the extension period the following efficacy variables will be analyzed

#### Safety variables

Primary safety variable:

Occurrence of treatment emergent AEs [TEAEs] overall and by injection cycle.

Secondary safety variables:

- Occurrence of treatment emergent AESIs [TEAESIs] overall and by injection cycle.
- Occurrence of treatment emergent SAEs [TESAEs] overall and by injection cycle.
- Occurrence of TEAEs related to treatment as assessed by the investigator overall and by injection cycle.
- Occurrence of TEAEs leading to discontinuation overall and by injection cycle.

#### Other variables:

- Vital signs (blood pressure, heart rate, body temperature) at screening, baseline, Visits weeks 4 and 16, during the main period and at each injection visit in the extension period and at the end-of-study visit Week 64.
- Body height and weight at screening, final visit of the main period Week 16, and the end-of-study visit Week 64.
- BMI, calculated from body weight and height, at screening, final visit of the main period Week 16 and the end-of-study visit Week 64.
- Clinical chemistry and hematology at screening, final visit of the main period Week 16, and the end-of-study visit Week 64.
- Severity of CP will be assessed by the Gross Motor Function Classification System (GMFCS) at baseline
- Results of dental and oral examination by a dentist at screening (considered as baseline value), in Week 4, at the final visit of the main period (week 16), at the final visit of the second injection cycle (week 32) and the end-of-study visit (week 64), in terms of adverse events: findings indicating a worsening of the subject's condition since screening are to be recorded as adverse events.
- Occurrence of antibodies against *Botulinum* toxin A in subjects'  $\geq$ 30 kg body weight.
- Number of subjects with suicidal ideation, suicidal behavior, and self-injurious behavior without suicidal intent during treatment based on the Columbia-Suicide Severity Rating Scale [C-SSRS]. This scale is used to assess suicidality prospectively in this clinical study at baseline and at each post-baseline site visit.

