Periodontal and dental diseases are known adverse reactions caused by iatrogenic xerostomia following salivary gland irradiation. Injections with *Botulinum* toxins into the salivary glands result in less severe and only temporary changes of periodontal or dental tissues. Thickened saliva resulting from salivary gland injection with *Botulinum* toxin was described for children, as causing worsening of swallowing, breathing or speaking [Erasmus 2010]. Human saliva serves multiple functions in the oral cavity, including moistening of food, facilitation of mastication and swallowing, and cleaning and lubrication of the oral mucosa.

Additionally, secretory immunoglobulin A (sIgA) content within the saliva protects the oral cavity, including dental structures, from bacterial growth and plaque formation (part

of the immune system), preventing dental decay and erosion. With reduced salivary flow rates resulting from the BoNT treatment, the concentration of sIgA increases in the saliva probably as a result of reduced saliva volume [Ellies 2002]. The lack of detrimental effect upon dental and oral health with long-term treatment of sialorrhea with BoNT has not been demonstrated, and, furthermore, both adults with Parkinson's disease and children with cerebral palsy are known to be at increased risk of dental and periodontal disease due to their disabilities in regular oral hygiene. Therefore, the FDA has recommended that a qualified dental health provider need to perform several oral examinations on study subjects during the trial.

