### **10.7** Other safety assessments

A dental and oral examination will be performed by a qualified dental health provider (minimum qualification: dentist) at screening (V1), V3 and V6 of the main study period, at V10 and at the-end-of-study visit (V18), or at the subject's last study visit if this is earlier. Results of dental and oral examination will be reported in terms of adverse events: findings indicating a worsening of the subject's condition since screening are to be recorded as adverse events.

Details are given in Appendices 16.4.1.

As part of the physical examination, particular attention will be paid to lungs in order to detect any signs of aspiration, at baseline and every subsequent visit.

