- If month, day and time are missing, but year is given and covering several OLEX cycles and the earliest possible OLEX cycle for assignment starts in the year before the AE start (but ends in the year of the AE start), month and day will be set to 1 and time to 00:00. If the earliest possible OLEX cycle for assignment starts in the year of the AE start, month/day/time will be set to month/day/time of the respective cycle start.

Calculation of time to duration of AEs [days]:

• The duration will be calculated as stop date - onset date + 1 for each episode of worsening of AE.

An overview summary table will be created for TEAEs and non-TEAEs displaying the frequencies and percentages of the following categories: "Any TEAE", "Any TEAE related to treatment", "Any TEAE of special interest", "Any TEAE of special interest related to treatment", "Any serious TEAE", "Any serious TEAE related to treatment", "Any TEAE leading to discontinuation", "Any TEAE leading to discontinuation related to treatment", "Any fatal TEAE" and "Any fatal TEAE related to treatment" for TEAEs and "Any non-TEAE", "Any non-TEAE", "Any serious non-TEAE", "Any non-TEAE", "Any serious non-TEAE", "Any non-TEAE leading to discontinuation" and "Any fatal non-TEAE" for non-TEAEs.

Incidences will be calculated for TEAEs, treatment-related TEAEs, serious TEAEs, related serious TEAEs, TEAEs leading to discontinuation, TEAEs of special interest at the system organ class level and at the preferred term level and will be presented by treatment, by injection cycle and overall (i.e. per period). TEAEs will also be presented by preferred term level, by treatment, injection cycle and overall. Additionally, TEAEs will be analyzed by worst intensity, by worst causal relationship and by worst outcome.

The number and percentage of subjects with at least one non-serious TEAE with incidence  $\geq =$  5% will be displayed by system organ class level and preferred term level.

In general, all safety analyses for OLEX will be performed overall and for the  $2^{nd}$ ,  $3^{rd}$  and  $4^{th}$  injection cycle. Only the number and percentage of subjects with at least one non-serious TEAE with incidence  $\geq = 5\%$  will be performed overall only.

Listings displaying incidences for TEAEs leading to discontinuation, serious TEAEs and TEAEs of special interest will also be provided.

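### Dental findings come from exams at unequal intervals but are tabulated by injection cycle, which inflates cycle 4, can move week-16 findings out of the placebo-controlled period, and leaves no dental summary in the SAP text

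*Protocol*

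**What the plan says.** **Purpose.** Protocol 4.2 explains why a dentist is involved: "The lack of detrimental effect upon dental and oral health with long-term treatment of sialorrhea with BoNT has not been demonstrated". It adds that the FDA recommended oral examinations by a qualified dental provider.

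**Schedule.** The synopsis (Other variables) sets exams at screening, weeks 4 and 16, and "at the final visit of the second injection cycle (week 32) and the end-of-study visit (week 64), in terms of adverse events". Sections 9.1.1.3 and 10.7 agree: screening, V3 (week 4), V6 (week 16), then "at V10 and at the-end-of-study visit (V18), or at the subject's last study visit if this is earlier". V10 is week 32 and V18 is week 64. V14, the end of cycle 3, is not on the list.

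**Capture.** There is no dental score. In the synopsis, "findings indicating a worsening of the subject's condition since screening are to be recorded as adverse events".

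**Analysis.** The primary safety variable is "Occurrence of treatment emergent AEs [TEAEs] overall and by injection cycle". SAP 7.5 says that incidences by system organ class and preferred term "will be presented by treatment, by injection cycle and overall (i.e. per period"). Cycles 2 to 4 are defined by an onset or worsening date on or after the date of the injection that opens the cycle.

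Dental results do not appear in protocol 12.3.6, nor in SAP 6.5.3, 6.6, 7.5 or 7.6. SAP section 8 lists other protocol variables that were moved, but does not mention dental results.

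**The concern.** A by-cycle table can be read as a time course only if events are equally likely to be found, and found equally promptly, in each cycle. For worsening that only a dentist would notice, this does not hold. Cycles 3 and 4 share one scheduled exam, 32 weeks after the previous one. What that exam finds is likely to be dated in cycle 4 unless the true onset can be established.

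The injection-day rule adds a second problem. The week-16 exam closes the only period with a placebo group, and it normally falls on the day of the first open-label injection. If a finding from that exam counts in the new cycle, it leaves the randomized comparison. In a child given placebo, it is then shown as arising under NT 201.

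Both effects bear on the question the exams were meant to answer: whether repeated treatment harms teeth and gums. A rise towards cycle 4 produced by the schedule looks the same as cumulative harm, and a thinned main period weakens the one controlled comparison.

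**Working it through.** The documents give no expected rate of dental worsening, so there is no figure of theirs to reproduce. The check uses the exam schedule and the SAP's cycle rules.

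**Inputs from the documents**
- Exams at weeks 0 (screening, taken as baseline), 4, 16, 32 and 64, giving intervals of 4, 12, 16 and 32 weeks.
- Four cycles of 16 weeks.
- V6/V6a, V10/V10a and V14/V14a normally on the same day (protocol 7.4).

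**Assumptions, not in the documents**
- A constant true rate of new dental worsening.
- A share *s* of findings carries its true onset date; the rest carry the exam date.

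**Which cycle gets an injection-day finding?** Three rules in SAP 7.5 bear on this.
- The cycle definitions place an event dated on the injection date in the new cycle.
- A missing start time on an injection day is set to the injection time, which also points to the new cycle.
- The special rule for an unclear OLEX cycle assigns the earliest possible cycle, which points the other way. It is worded for OLEX cycles, so whether it reaches the week-16 boundary is not stated.

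The two time and date replacement rules are introduced for calculating AE duration. The detailed classification rules are in SAP Appendix 1, which is not in the file. Both readings are therefore shown.

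**Formula.** Count in a cycle relative to truth = *s* + (1 − *s*) × (weeks assigned to that cycle / 16).

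Weeks assigned to cycles 1 to 4:
- Earlier-cycle reading: 4 + 12 = 16, then 16, 0 and 32.
- New-cycle reading: 4, 12, 16 and 32.

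| Reading | *s* | Cycle 1 | Cycle 2 | Cycle 3 | Cycle 4 |
|---|---|---|---|---|---|
| Earlier cycle | 0 | 1 | 1 | 0 | 2 |
| Earlier cycle | 0.5 | 1 | 1 | 0.5 | 1.5 |
| Earlier cycle | 0.75 | 1 | 1 | 0.75 | 1.25 |
| New cycle | 0 | 0.25 | 0.75 | 1 | 2 |
| New cycle | 0.5 | 0.63 | 0.88 | 1 | 1.5 |
| New cycle | 0.75 | 0.81 | 0.94 | 1 | 1.25 |

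The truth is 1 in every cell. Cycle 4 is inflated by the same amount under both readings; the readings differ in where the shortfall falls.

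**Counting children instead of events.** With risk p per 16 weeks, the 32-week risk is 1 − (1 − p)². For p = 1%, 5%, 10% and 30% this gives 1.99%, 9.75%, 19% and 51%. The ratios to p are 1.99, 1.95, 1.90 and 1.70.

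**Main period, new-cycle reading.** The share of findings that leaves is (1 − *s*) × 12/16. This is 75% at *s* = 0 and 37.5% at *s* = 0.5, in both arms.

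**Wholly missing start date.** For an event that ends in the extension, the start is set to the first OLEX injection, which is cycle 2. Cycle 4 is then not inflated, but a finding from cycle 3 or 4 is still misplaced.

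**Effect on the any-TEAE row.** Take the earlier-cycle reading with *s* = 0 and an assumed risk q of any other TEAE per cycle. The row shows 1 − (1 − q)(1 − x), where x is the dental risk shown.
- q = 20%, dental risk 10%: true 28.0%; cycle 3 shows 20.0% and cycle 4 shows 35.2%.
- q = 40%, dental risk 2%: true 41.2%; cycle 3 shows 40.0% and cycle 4 shows 42.4%.

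Over q of 20–40% and dental risk of 2–10%, the shift is about 1 to 8 points down in cycle 3 and 1 to 7 points up in cycle 4.

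**The case against.** The strongest defence is that the plan does what the protocol announces. Dental results are defined in terms of adverse events, so the adverse event tables are their analysis, and the main-period table compares NT 201 with placebo. Adverse events are collected at every visit by spontaneous report, inquiry and examination, with dates of onset and worsening recorded (protocol 10.1). Cycles are assigned by onset, not by detection. Children who leave early are examined at their last visit.

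Much of this stands. Reports between exams and true onset dates shrink the artefact, as the rows for *s* = 0.5 and 0.75 show, but they do not remove it. The protocol requires a dentist's examination because ordinary inquiry is not an equivalent way to find dental disease. The general tables also leave open which period a week-16 finding belongs to.

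A reader might infer more than the documents support:

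- *Cycle 3 will be near zero and cycle 4 double.* This needs every finding dated to the exam, none reported between exams, and V10 findings counted in cycle 2. With V10 and V10a on one day, the SAP's cycle definition puts those findings in cycle 3, which is then about right, and cycle 1 is the depleted one.
- *The by-cycle adverse event tables are distorted as a whole.* Only dental terms are affected. The any-TEAE row moves by a few points under the assumed rates.
- *The dental analysis was dropped.* The SAP text has no dedicated dental table, but the table shells (SAP Appendix 1), protocol Table 6 and the dental appendix are not in the file. Dental events do enter the general tables.

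**Conclusion.** The concern holds for dental findings. Exam spacing is unequal, the planned by-cycle tables ignore it, and the SAP text neither settles the cycle of a finding made on an injection day nor plans a dental summary.

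For findings dated to the exam, cycle 4 is inflated under either attribution reading. The factor is up to about 2 and is an upper bound; it falls to about 1.5 if half of the findings carry their true onset date. Under the new-cycle reading, up to three quarters of main-period dental findings could be counted in the open-label period.

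These sizes rest on a constant true rate, 16-week cycles, visits held on the same day and an assumed dating share; none can be checked against data in the documents. The co-primary efficacy analyses are not touched. The point is worth fixing before unblinding because the dental question is a stated reason for the exams.

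**What to change.** In SAP 7.5, add one descriptive dental/oral table by examination (weeks 4, 16, 32 and 64):

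- Define dental/oral events by a preferred-term list fixed before unblinding.
- Assign each event to the exam interval in which it is dated. A finding dated to an exam belongs to the interval that the exam closes, so week-16 exam findings count in the main period.
- For each exam, give the number of children examined and the number with any new worsening since screening.
- At weeks 4 and 16, give the NT 201 v placebo risk difference with a 95% CI for ages 6–17 years.
- Report weeks 32–64 as one interval, not split into cycles 3 and 4.

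Keep all dental events in the by-cycle TEAE tables, since removing them would take real events out of the primary safety variable. Footnote the unequal exam spacing there. A new field on the adverse event page is not proposed, because at the date of this SAP it would have to be filled in retrospectively.

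An extra exam at week 48 would not be enough by itself. If injection-day findings go to the new cycle, the pattern stays 0.25 / 0.75 / 1 / 2, because the week-48 and week-64 findings (16 + 16 weeks) both fall in cycle 4.

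The cost is one table, a term list and a footnote, with no added visits or exams. The table assumes that the database shows whether each exam took place. If it does not, attendance at the visit has to serve as the denominator and be labelled as such.
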